6. SUBJECT SELECTION CRITERIA

Inclusion Criteria

- o Male or female participants between 6 and 17 years of age
- Fulfills diagnosis of autism spectrum disorders by meeting DSM-IV-TR PDD diagnostic criteria of autistic disorder, Asperger's disorder, or PDD-NOS as established by clinical diagnostic interview
- o Participants with a score of ≥13 on the Pediatric Anxiety Rating Scale (PARS)

- Participants with a score of ≥60 or more on the Anxiety/Depression subscale of CBCL and CGI-Anxiety severity of ≥ 4
- Subjects can be taking psychotropic medications if they have been on the medication for at least 4 weeks prior to initiating study treatment and if they are on a stable dose, provided the medication is not listed in the Concomitant Medications section of the protocol.
- o Subjects with disruptive behavior disorders, mood, or psychosis will be allowed to participate in the study provided they do not meet any exclusionary criteria

Exclusion Criteria

- o I.Q. < 70
- o DSM-IV-TR PDD diagnoses of Rett's disorder, and childhood disintegrative disorder
- o History of active seizure disorder (EEG suggestive of seizure activity and/or history of seizure in last 1 month)
- o Subjects with a medical condition or treatment that will either jeopardize subject safety or affect the scientific merit of the study, including:
 - o Pregnant or nursing females
 - o Organic brain disorders
 - o Uncorrected hypothyroidism or hyperthyroidism
 - o Clinically significant abnormalities on ECG (e.g., QT prolongation, arrhythmia)
 - o History of renal or hepatic impairment.
- o Clinically unstable psychiatric conditions or judged to be at serious suicidal risk
- o Current diagnosis of schizophrenia or bipolar disorder
- o History of substance use (except nicotine or caffeine) within past 3 months or urine drug screen positive for substances of abuse
- o Current treatment with medication with primary central nervous system activity (as specified in the Concomitant Medication section of the protocol)
- o A non-responder or history of intolerance to buspirone, after treatment at an adequate dose and duration as determined by the clinician
- Subjects currently taking monoamine oxidase inhibitors (MAOI) and/or CYP3A4 inducers or inhibitors including nefazodone, diltiazem, verapamil, erythromaycin, itraconazole, or rifampin.

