We anticipate that subjects may enter this trial following completion of/withdrawal from other protocols in our office, and that there may be procedural overlap. So as to not burden subjects/parents/guardians with redundant time commitments, we will use the following *diagnostic* data previously collected: If a subject has completed an evaluation with one of the study clinicians within the previous three years or an informant has completed the SRS-2 within the six months prior to entrance into this study, subjects will not be asked to repeat any overlapping diagnostic procedures. We will use the study diagnostic data that had been previously collected so as to not burden the subject with redundant time commitments. However, the study clinician will review the interval time period to assess for clinically significant medical or psychiatric history, to ensure that the subject meets appropriate study entrance criteria.

If the subset of scales assessing intelligence (WASI-II) in the neuropsychological battery has been completed within 12 months prior to entrance into this study, subjects will not be asked to repeat these procedures. We will use the diagnostic data previously collected so as not to burden the subject with redundant time commitments.

Although every effort will be made to encourage subjects to keep regularly scheduled appointments, in the event that a subject is unable to come into the office within a reasonable timeframe of a scheduled visit, and the treating research clinician feels that subject safety will not be jeopardized by doing so, the clinician can conduct the visit with the subject and parent/guardian over the phone. The clinician will complete the phone visit form for all phone visits that occur. This will ensure that each subject will be continuously monitored by the clinician throughout the course of the study despite unforeseen scheduling circumstances. The study evaluation visit, the baseline visit or the final study visit may be not conducted over the phone. Additionally, phone visits may not occur for two consecutive visits.

Evaluation and Characterization: Week 99

After providing study information and obtaining IRB-approved informed consent and assent, participants will undergo an initial screening assessment consisting of a brief demographic interview (collecting information regarding socioeconomic status and history of head injury or trauma), psychiatric and medical history, and assessment

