measures (CBCL, PARS, and CGI-Anxiety). Eligible subjects will be administered a detailed assessment battery consisting of diagnostic measures (complete psychiatric evaluation including MGH-ASD-SCL), cognitive assessments (WASI-II and DANVA 2), measures of psychosocial functioning (SAICA and M-FES), and physical assessment measures (complete physical examination including height, vitals, ECG, urine screens, and blood tests). Screening (week 99) procedures can occur over 2 days (within the three week screening window).

Washout Period

After the screening period, subjects who are currently taking prohibited medications (refer top section on the, "Concomitant Medications/Treatments") must discontinue the use of their medication to be eligible for participation in this study. Medication washout is recommended by our clinicians to participants, their parent/guardian, and current providers – this is done according to a case-by-case assessment, considering the duration on drug, the dose, and the adverse effects associated with the treatment and effects of stopping that medication/treatment. Our office does not take over care for the patient, but remains available during this time period. The washout schedule will be discussed with the participant, their parent/guardian, and current providers.

Treatment Trial Phase: Weeks 0 through 8

Participants who fulfill the inclusion and exclusion criteria will be treated with buspirone for a period of 8 weeks. Subjects will be evaluated at weekly intervals during titration phase (4 weeks from baseline) and thereafter every 2 weeks during the maintenance phase of the trial. Study visits will have a visit window of +/- 2 days to facilitate scheduling. Each visit will assess drug efficacy (CGIs and GAF), tolerability (assessing for treatment-emergent adverse-events), and safety (vital signs including weight). At baseline, midpoint (week-4), and endpoint, the PARS, MASC, SRS-2, MGH-SECS-C and -I, BRIEF, CDRS-R, YMRS, CY-BOCS-PDD, and PQ-LES-Q assessment measures will be administered. The CBCL will also be administered at weeks 4 and 8/drop-visit. At endpoint (completion/drop-visit), participants will be reevaluated on cognitive (DANVA 2) and physical assessment measures (complete physical examination including vitals, ECG, blood tests, and urine screening).

Study Discontinuation

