Buspirone will be administered in divided dosage. During the titration phase, the total dose of buspirone will be increased at each visit and on the 4th day after each visit by 5 mg.

galaonnoo ao	Johnson	in allo i nyolola								
Buspirone Flexible Titration Schedule										
Visit	Week	Day	Maximum Total Dose (mg/day)							
1	0	1	10							
	0.5	5	15							
2	1	8	25							
	1.5	12	30							
3	2	15	40							
	2.5	19	45							
4	3	22	55							
	3.5	26	60							
5	4	28	Maintained on the maximum achieved dose							

The study buspirone titration schedule, detailed below, is based on treatment guidelines described in the Physicians' Desk Reference [45].

Buspirone will be available in four different strengths: 5,10,15, and 30 mg. Ten days worth of study medication will be dispensed for weekly visits and 20 days worth of medication will be dispensed for biweekly visits. To assess and ensure drug

accountability and compliance, study medication will be returned, counted, and redispensed every visit by the study coordinator.

Concomitant Medications / Treatments

A detailed past and present treatment history (pharmacological / non-pharmacological) will be taken as part of initial evaluation. Following are the concomitant medications/treatments guidelines:

- o Participants on stimulant medication must be on a stable dose for at least 2 weeks prior to baseline.
- o Subjects may take melatonin (up to 3mg) or Benadryl (up to 50 mg) at bedtime as needed (prn) for insomnia.
- Non-pharmacological treatments such as supportive individual, family, or group therapy will be permitted provided they were in place for a substantial period of time (> 1 month) prior to study participation and remain unchanged during the course of the trial.
- o No new non-pharmacological treatments may be initiated during the course of the trial.
- o Subjects may not take monoamine oxidase inhibitors (MAOI) and CYP3A4 inducers or inhibitors including: nefazodone, diltiazem, verapamil, erythromycin, itraconazole, rifampin or grapefruit juice

8. ASSESSMENTS (see protocol schedule)

A. Diagnostic Assessments

Administered at Week 99

 MGH ASD Symptom Checklist (MGH-ASD-SCL): The spectrum of ASD symptoms will be screened by using clinician administered MGH-ASD-SCL. This screening instrument adopted items from DSM-IV diagnostic criteria for PDD and assesses for the individual core domains and associated features of ASD.

B. Psychosocial Assessment Measures

Administered at Week 99

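### The rule allowing reuse of an SRS-2 up to six months old can displace the only pre-treatment SRS-2, which is the baseline of a secondary outcome

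*Combined protocol and SAP*

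**What the plan says.** Section 7 (Design) explains why data may be reused: "We anticipate that subjects may enter this trial following completion of/withdrawal from other protocols in our office". To spare families repeated work, it names data of a diagnostic kind that will be taken from the earlier contact. One item is an evaluation by a study clinician in the previous three years. The other is an informant's SRS-2, under this rule: "completed the SRS-2 within the six months prior to entrance into this study, subjects will not be asked to repeat any overlapping diagnostic procedures". A separate paragraph treats the WASI-II: if that was "completed within 12 months prior to entrance into this study, subjects will not be asked to repeat these procedures".

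The same section then sets the SRS-2 schedule for the treatment phase: "At baseline, midpoint (week-4), and endpoint, the PARS, MASC, SRS-2, MGH-SECS-C and -I, BRIEF, CDRS-R, YMRS, CY-BOCS-PDD, and PQ-LES-Q assessment measures will be administered". Section 8.D and the schedule table agree on weeks 0, 4 and 8. The screening battery is described as "diagnostic measures (complete psychiatric evaluation including MGH-ASD-SCL), cognitive assessments (WASI-II and DANVA 2" and other measures, with no SRS-2 among them. Section 8.A (Diagnostic Assessments) lists only the MGH-ASD-SCL.

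The secondary outcomes in Section 7 use the SRS-2 to assess core features of ASD. Section 9 (Data Analysis) compares week 0 with week 8 by paired tests. It argues that time-varying factors will matter little because the trial is short.

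**The concern.** The waiver names the SRS-2, but the only pre-treatment SRS-2 in the protocol is the week-0 efficacy baseline. Site staff who follow the waiver literally would skip that form and use an old score in its place. The subject's change score would then include whatever happened between the old form and week 0, and all of it would be counted as change on buspirone. With no control group, nothing separates the two.

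The protocol's own rules leave room for such change:

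- Psychotropic medication is allowed if "they have been on the medication for at least 4 weeks prior to initiating study treatment" at a stable dose.
- For stimulants, Section 7 says "Participants on stimulant medication must be on a stable dose for at least 2 weeks prior to baseline".
- After screening, subjects on prohibited medication "must discontinue the use of their medication to be eligible for participation in this study".
- Subjects may arrive from other protocols, and the text does not say whether those involve treatment.

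A form completed at week 0 comes after any of these changes. A form completed months earlier may not.

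**Working it through.** **1. Which SRS-2 could the waiver replace?**

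| Place | SRS-2 at screening (week 99) | SRS-2 at week 0 |
|---|---|---|
| Section 7, screening battery | not listed | – |
| Section 7, treatment phase | – | yes |
| Section 8.A, Diagnostic Assessments | not listed | – |
| Section 8.D, severity of core features | not listed | yes |
| Schedule table | empty cell | marked |

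Three SRS-2 administrations are scheduled (weeks 0, 4 and 8). One is before treatment and none is at screening, so the only form an old SRS-2 could stand in for is week 0. The interval review that Section 7 requires for reused data serves the entry criteria, not the outcome baseline.

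**2. Length of the comparison.** Inputs: look-back of six months, taken as 26 weeks (Section 7); screening up to 3 weeks (Section 3); treatment 8 weeks. The protocol does not define entrance, so both meanings are shown.

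- Entrance = week 0: 26 + 8 = 34 weeks, which is 34/8 = 4.25 times the planned interval. Pre-treatment share 26/34 = 76%.
- Entrance = start of screening: 26 + 3 + 8 = 37 weeks, which is 37/8 = 4.6 times. Pre-treatment share 29/37 = 78%.

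Weeks before week 0 not covered by a stability rule: 26 − 4 = 22 or 29 − 4 = 25 for psychotropics in general; 26 − 2 = 24 or 29 − 2 = 27 for stimulants. The washout length is not given and is not added.

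**3. Illustration of the effect on the test.** The documents give no number of waived subjects, no drift and no SRS-2 SD. Assumptions: n = 10 analysed (the exposure goal in Section 4); normal paired changes with SD 1; k subjects with a reused form, each with drift d = 0.5 or 1 SD; exact two-sided signed-rank test at 0.05; true improvement 0.9 SD for power; 200,000 simulated trials per cell. The test rejects if W ≤ 8 or W ≥ 47. Its exact size is 2 × 25/1024 = 4.88%. Power with no reused form is 69.7%.

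*Drift equally likely up or down for each waived subject* (expected shift 0; standard error of the mean change multiplied by √(1 + k·d²/n), that is 1.01 to 1.22):

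| k | Null rejection | Power, d = 0.5 | Power, d = 1 |
|---|---|---|---|
| 1 | 4.8–4.9% | 68.7% | 65.6% |
| 3 | 4.8–4.9% | 66.9% | 58.4% |
| 5 | 4.8–4.9% | 64.7% | 52.2% |

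*Drift in the same direction for all waived subjects* (mean shift d·k/n, from 0.5 × 1/10 = 0.05 to 1 × 5/10 = 0.5 SD):

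| k | Null rejection, d = 0.5 | Null rejection, d = 1 | Power at d = −1 / −0.5 / +0.5 / +1 |
|---|---|---|---|
| 1 | 5.0% | 4.9% | 55.7 / 64.0 / 73.5 / 75.6% |
| 3 | 6.4% | 9.6% | 30.6 / 52.3 / 80.7 / 86.3% |
| 5 | 9.5% | 20.7% | not run |

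Positive d means drift that looks like improvement.

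**The case against.** The best defence is that the protocol already settles this. Section 7, Section 8.D and the schedule table place the SRS-2 at week 0 without conditions, and Section 9 defines the baseline as week 0, before treatment. The waiver is limited to diagnostic procedures, with that word emphasised, and Section 8 files the SRS-2 as a severity measure. Grammatically, an earlier SRS-2 is one of two triggers for the waiver, not the thing waived. In the WASI-II paragraph the named test itself is what is not repeated. So the SRS-2 clause may simply be loose wording.

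This reading is reasonable and may be what the authors meant, but it does not close the question:

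- It leaves the SRS-2 clause with no scheduled SRS-2 to save anyone from completing.
- Section 7 uses *diagnostic* loosely. It calls the WASI-II results diagnostic data, yet the screening battery lists that test as a cognitive assessment.
- Unconditional scheduling does not rule out a waiver. The WASI-II is scheduled just as firmly and is expressly waived.
- Week 0 is not a strict baseline for every outcome. The DANVA 2 is an outcome whose only pre-treatment administration is at screening.

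Two parts of the defence stand in full. The text is ambiguous and does not prove that old scores will be used. The simulated figures are illustrative: the worst need three to five waived subjects all drifting the same way, and this pilot makes no power claim.

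**Conclusion.** The concern holds. The protocol contains a rule that, applied to the form it names, gives the wrong baseline, and no passage prevents that application. The firm figure is the interval: up to 34 or 37 weeks against 8 planned, if the waiver is applied. The effect on the SRS-2 result is unknown, because it depends on how many subjects are waived and how far they drifted. Under the stated assumptions a single reused form does little. Drift in mixed directions costs power but leaves the false-positive rate alone. False positives rise only if several waived subjects drift the same way.

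The reach is limited. It concerns one of the four core-feature measures in a hypothesis-generating pilot. The CY-BOCS-PDD and both MGH-SECS scales, like the primary PARS and CGI-Anxiety, are not named in the waiver. It should be fixed, but it does not threaten the trial's main result. Confidence is medium because a harmless reading exists.

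**What to change.** Add to Section 7: *A previously completed SRS-2 may be used for diagnostic characterisation only; a new SRS-2 is completed at week 0, before the first dose, for every subject, and only that score is the efficacy baseline.* If the narrow reading was always intended, this merely confirms it.

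If any enrolled subject already lacks a week-0 form, report how many, and show the SRS-2 change with and without them.

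The cost is one sentence and the lost time saving on one parent questionnaire that is already in the week-0 schedule. The analysis without those subjects may be descriptive only. The smallest two-sided signed-rank p-value is 2/2ⁿ, which is 2/32 = 0.0625 with 5 pairs and 2/64 = 0.031 with 6, so with 5 or fewer pairs the test cannot reach 0.05.

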9. DATA ANALYSIS

Considering our open-label single group design, we will rely on comparisons of the participants' performances at baseline (week 0) prior to the initiation of treatment relative to their scores at the last assessment (week 8). Thus, statistics for paired samples will be utilized. This design largely protects against the bias introduced by confounding factors. That is, since the same participants are tested on two occasions, all static confounding factors are perfectly balanced, and can have no impact on the findings. Bias can still result from time-varying factors that are not associated with the outcomes, but we are confident that any such factors will have a minimal impact on this study, considering the duration of the trial. Specifically, we will employ Wilcoxon signed rank tests for continuous or discrete outcome measures, and McNemar's test for binary outcomes. These tests are free from assumptions regarding the distribution of the outcome variables, which is appropriate since the scales we are proposing to utilize are not considered to have Gaussian distributions, and will not be amenable to parametric methods.

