4. SOURCE OF SUBJECTS

We plan to enroll 15 youth in order to achieve the goal of exposing 10 subjects to the study medication. We will recruit subjects both internally and externally. Participants will be recruited from the pool of existing patients and new referrals to the Pediatric Psychopharmacology Program and the Alan and Lorraine Bressler Clinical and Research Program for Autism Spectrum Disorders at the MGH, as well as from the Child and Adolescent Psychiatry Department at MGH.

The Bressler clinic is a specialized ambulatory care program, devoted to the assessment and treatment of youth and adults with ASD. The patient population served by the MGH derives from Boston and its suburbs. Approximately 50% of referrals have never been diagnosed or treated. The 3,000 youth that use this clinic make approximately 9,000 visits each year.

If a potential subject's clinician ascertains that the patient has an interest in study participation, the clinician will offer contact information for the study to the patient and/or their parent/guardian. The patient and/or their parent/guardian can then contact the study coordinator for more information on the study. If the patient's physician is a

member of study staff, the patient and his/her family will also be offered the opportunity to speak with another study physician who is not their treating clinician to review study details and consider participation. Clinical records are not scanned in order to recruit subjects.

Subjects may also be recruited from our department's screening protocol entitled, "A General Screening Protocol for Child and Adolescent Research Studies in the Pediatric Psychopharmacology Program", (#2014-P-001103). After participating in the general screening protocol, subjects may be identified as potentially eligible for this study and will be contacted via telephone by our study staff within 7 business days to assess their interest and to complete a specific phone screen for this study. When a member of our study staff telephones the potential subject they will use the already IRBapproved Buspar OL Telephone script. 5 attempts will be made to reach the potential subject before they will be considered uninterested and will not be contacted again by our program regarding this study. Participants, and their parent, who meet eligibility criteria will then be brought in to meet with a study clinician who will explain the study in detail and complete the informed consent process.

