7. DESIGN

This proposal seeks to complete an 8-week open-label trial to study the efficacy, tolerability, and safety of buspirone for the treatment of the features of anxiety in youth with ASD. In this study, we propose to examine ASD youth ages 6-17 years with significant anxiety features.

Outcome measures

Primary outcome measures: Efficacy will be assessed by reduction in anxiety symptom severity as measured by change from baseline on the PARS and CGI-Anxiety-Improvement scores. Responders are defined as \geq 30% reduction on the PARS and a score \leq 2 on the improvement subscale of CGI-Anxiety, i.e., "much" or "very much improved."

Secondary outcome measures will assess the impact of buspirone therapy on the following parameters:

I. Safety and tolerability assessed by monitoring:

- 1. For treatment-emergent adverse events
- 2. Vital signs (blood pressure, height and weight)

- 3. Electrocardiogram (ECG)
- 4. Hematological parameters
- 5. For the emergence or worsening of:
 - a. Anxiety symptoms assessed by PARS and CGI-Anxiety
 - b. Depressive symptoms assessed by CDRS-R and CGI-Depression
 - c. Irritability/mania symptoms assessed by YMRS and CGI-Mania
 - d. Inattention/hyperactivity symptoms assessed by CGI-ADHD
 - e. Repetitive/ritualistic behaviors assessed by CY-BOCS-PDD and CGI-OCD

II. Core features of ASD assessed by SRS-2, CY-BOCS-PDD, and MGH-SECS-C and -I III. Associated features of ASD assessed by YMRS, CDRS-R, and respective CGI-

- Improvement subscale
- IV. Cognitive functioning assessed by BRIEF and DANVA 2.

This study plans to recruit 15 subjects with ASD between 6-17 years of age with clinically significant and functionally impairing features of anxiety as rated by parent (significant score on the Child Behavior Checklist [CBCL] subscales for anxiety/depression) and clinician ($a \ge 4$ on severity subscale of Clinical Global Impression Scale [CGI] for anxiety).

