Participants will be withdrawn from the study if they experience significant worsening of symptoms, or if the subject or their family decides to withdraw. A subject may be withdrawn from the study at any time if any of the following conditions are met:

- Worsening of PDD, ADHD, OCD, anxiety, depression, or mania, as reflected by respective Clinical Global Improvement score of 6 (Much worse) or 7 (Very Much Worse) for 2 visits in a row.
- Subjects who experience intolerable adverse effects, and/or clinically significant laboratory values inconsistent with continuation in the study.
- Unstable psychiatric condition that clinically requires 1) a change in stable dose of concomitant psychotropic medications or 2) subjects requiring inpatient psychiatric admission.
- Emergent suicidality
- Active substance abuse

- Pregnancy
- Allergic drug reaction
- Non-compliance (less than 70% compliance for 2 visits or longer)
- Failure to return medication or dosing diary for 2 consecutive visits
- Failure to keep study appointments for more than 2 consecutive visits without justification
- Clinical judgment of the investigator
- Withdrawal of consent

If study participation is discontinued for safety reasons, participants will be offered three follow-up clinical visits, allowing adequate time for appropriate psychiatric referrals to treaters in their communities.

Study Medication

At each visit, measures of safety and effectiveness will be administered. Buspirone will be titrated to the maximum daily dose during the first four weeks of the trial (dose titration phase). Week-4 onwards, subjects will be maintained on maximum achieved dose till the end of the trial (dose maintenance phase).

Dose titration phase: Titration of buspirone will follow the flexible titration schedule with an option for slower titration, holding at lower dose, or lowering the dose based on tolerability and response to buspirone as per clinician judgment. Dose will be adjusted upward per titration schedule provided the treatment is well tolerated and the response is insufficient (CGI-Improvement>2).

Dose maintenance phase: During the maintenance phase, buspirone will be maintained on the maximum achieved dose. As a one-time option during the maintenance phase, the dose of the study medication can be decreased by a maximum of 10 mg based on tolerability to buspirone per clinician judgment.

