 Wechsler Abbreviated Scale of Intelligence Scale (WASI-II) Vocabulary and Matrix Reasoning subtests: This scale meets the demand for a quick reliable measure of intelligence in clinical, educational, and research settings and will provide a Full Scale IQ.

Administered at Weeks 99 and 8/drop-visit

3. Assessment of Social Cognition

 Diagnostic Analysis of Nonverbal Accuracy Scale (DANVA 2): Child Faces and Child Paralanguages subtests. This assessment consists of 2 tasks of social competence assessing participant ability for recognizing feelings expressed through faces and paralanguage by children: Both subtests have been standardized and have acceptable internal consistency and reliability. This test can be administered for testing social competence in children as young as 3 years of age.

D. Quantitative Scalar Assessments

Administered Weeks 0-8/drop-visit

Severity assessment of ADHD, PDD, Psychosis, Mania, Depression, Anxiety, and OCD

NIMH Clinical Global Impression Scale (CGI): The CGI is a measure of illness severity, improvement, and efficacy of treatment. The score for severity ranges from 1 (normal, not at all ill) to 7 (among the most extremely ill subjects). Improvement ranges from 1 (very much improved) to 7 (very much worse). And lastly, the effectiveness index measures to what extent the subject is experiencing therapeutic effects as well as the level of adverse events. The CGI scales will be used for the assessment of PDD, ADHD, OCD, psychosis, mania, depression, and anxiety.

Severity assessment of Anxiety

Administered at screening (Week 99), baseline (Week 0) midpoint (Week 4), & endpoint (Week 8/drop-visit)

Pediatric Anxiety Rating Scale (PARS): The PARS is a clinician-rated scale, to be used with parent and children. It has 2 sections: a symptom checklist and severity items. The symptom checklist is used to determine the child's repertoire of symptoms during the past week. The 7 severity items are used to determine severity of symptoms and the PARS total score. The total score for the PARS is derived by summing the 7 severity items; total score ranges from 0 to 35.

Administered at baseline (Week 0), midpoint (Week 4), and endpoint (Week 8/drop-visit)

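### By implication, Section 9 gives McNemar's test to responder status, which no subject can meet at week 0; a response rate with an exact confidence interval should replace it

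*Combined protocol and SAP*

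**What the plan says.** Section 9 (Data Analysis) is a single paragraph. It compares subjects at "baseline (week 0) prior to the initiation of treatment relative to their scores at the last assessment (week 8", concludes that paired statistics are appropriate, and says "we will employ Wilcoxon signed rank tests for continuous or discrete outcome measures, and McNemar's test for binary outcomes". It does not say which outcomes are binary or which version of McNemar's test is meant. It mentions no response proportion, confidence interval, reference rate, alpha or sidedness.

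Section 7 (Design, primary outcome measures) bases efficacy on "change from baseline on the PARS and CGI-Anxiety-Improvement scores". The same paragraph defines a responder as a subject with at least a "30% reduction on the PARS and a score" of 2 or less on the CGI-Anxiety improvement subscale. No other binary efficacy outcome is defined anywhere.

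Section 8.D gives the PARS schedule as "Administered at screening (Week 99), baseline (Week 0) midpoint (Week 4), & endpoint (Week 8/drop-visit", so a rating is planned at the visit where a subject drops out. Section 4 plans to enroll 15 youth "in order to achieve the goal of exposing 10 subjects to the study medication". Section 2 describes the study as a pilot meant to supply hypotheses for a larger randomized trial.

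**The concern.** McNemar's test compares how often a binary state is present at two times in the same subjects. It is informative when subjects can move in both directions. Responder status is not such a state: it is defined by change since week 0, so at week 0 it is absent for everyone by definition. Pairing it with week 8 compares the observed responders with a zero that is built in.

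Response is part of the primary efficacy definition. If Section 9 is followed as written, it is summarised by a p-value against a benchmark nobody would propose. A team planning the next trial needs the proportion responding and its uncertainty, and Section 9 plans neither. The denominator is also open, with 15 to be enrolled and 10 to be exposed, as is the handling of subjects who stop before week 8.

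**Working it through.** The plan gives no response rate, power or McNemar figure, so there is nothing of its own to reproduce.

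**Inputs.** The responder definition is from Section 7. The pairing of week 0 with week 8 is from Section 9. The group sizes are from Section 4: n = 10 is the planned number exposed, and n = 15 applies if all enrolled subjects were dosed. A two-sided 0.05 level is my assumption, for illustration only.

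**Step 1: the table.** At week 0 each subject's PARS reduction from baseline is 0%, below the 30% required, whatever CGI score is recorded. All n subjects are therefore non-responders at week 0. Let r be the number of responders at week 8. Then:

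- non-responder to responder: r
- responder to non-responder: 0
- non-responder at both: n − r

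**Step 2: the null.** McNemar's null is that the two kinds of change are equally likely. One kind is impossible, so the null requires the other to have probability zero, that is, a week 8 response rate of zero. A single responder rules that out, yet with r = 1 the exact p is 2 × (1/2) = 1. The p-value is not a useful measure of evidence about response.

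**Step 3: the p-values.** With discordant counts (r, 0), two-sided:

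- exact conditional: p = 2 × (1/2)^r, capped at 1
- mid-p: p = (1/2)^r
- asymptotic: chi-square = r on 1 df
- continuity-corrected: chi-square = (r − 1)²/r on 1 df

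| r | exact conditional | mid-p | asymptotic | continuity-corrected |
|---|---|---|---|---|
| 4 | 0.125 | 0.0625 | 0.046 | 0.134 |
| 5 | 0.0625 | 0.031 | 0.025 | 0.074 |
| 6 | 0.031 | 0.016 | 0.014 | 0.041 |

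None of these formulas contains n. The smallest r with p below 0.05 is 6 (exact), 5 (mid-p), 4 (asymptotic) and 6 (continuity-corrected). With the version unstated, four or five responders could fall on either side of that illustrative level.

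**Step 4: the exception.** The exact unconditional test maximises the p-value over the unknown probability of a discordant pair, and it does depend on n:

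| r | n = 10 | n = 15 |
|---|---|---|
| 4 | 0.053 | 0.050 (0.0503) |
| 5 | 0.026 | 0.035 |
| 6 | 0.021 | 0.014 |

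The smallest r below 0.05 is 5 at both sizes.

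**Step 5: what an estimate would show.** The exact (Clopper-Pearson) 95% limits are the 2.5% point of Beta(r, n − r + 1) and the 97.5% point of Beta(r + 1, n − r). For r = 6:

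- 6/10 = 60%, limits 0.262 and 0.878
- 6/15 = 40%, limits 0.163 and 0.677

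The exact conditional p is 2 × (1/2)^6 = 0.031 in both cases. The two results would mean different things for planning a trial, and the test does not tell them apart.

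**The case against.** The strongest reply is that Section 9 never names responder status. Its wording covers all binary outcomes, and safety is an outcome too. ECG, blood tests and urine drug screens are done at screening and at the end, and a normal/abnormal or positive/negative state on these could be present at both visits, where McNemar's test is valid. This stands in part. A reader might infer that the plan expressly commits to McNemar's test for response; it does not, and the link is by implication. However, the plan does not dichotomise those safety measures, and their pre-treatment value is from screening, not week 0. If the test was meant only for them, the responder outcome has no stated analysis, and the same change to Section 9 is needed.

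A second reply is that Section 9 lists no descriptive statistics for any outcome, and that anyone who defines responders will count them. That is fair: silence is weak evidence that the rate would go unreported. It still leaves the denominator and the treatment of dropouts to be settled after the data are seen.

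A third is that this is a small pilot and nothing hangs on the p-value. That stands, and it limits the importance of the point.

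A reader might also infer that the p-value ignores n in every version of the test. Step 4 shows otherwise. The empty discordant cell and the zero-response null do hold in every version.

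**Conclusion.** The point holds. As written, and on the reading that responder status is the binary efficacy outcome meant, Section 9 tests response against a null of zero. In the exact conditional, mid-p, asymptotic and continuity-corrected versions the result depends only on the number of responders; in the exact unconditional version it depends slightly on n as well.

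The consequence is limited, and the change is worth making mainly because it is nearly free. A reader might infer that the trial's efficacy conclusion is unsound. The documents do not support that: no alpha or go/no-go rule uses this p-value, the signed-rank test of PARS at week 0 against week 8 is unaffected, and the proportion can be calculated from data already to be collected.

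The conclusion rests on the Section 7 definition and the Section 9 pairing. The 0.05 level and the choice of six responders are illustrations, not features of the plan.

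**What to change.** In Section 9, replace McNemar's test for responder status with text to this effect: *The response rate is the number of responders divided by all dosed subjects, reported with an exact 95% confidence interval.* Add a sentence stating in advance how dosed subjects without a week 8 rating are counted, for example as non-responders. This is a separate choice and should say whether a drop-visit rating may be used, since Section 8.D provides for one and Section 9 refers only to week 8.

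Keep McNemar's test only for binary states that can be present at both visits; name those variables and the version of the test. If a test of response is wanted, use an exact binomial test against a reference rate justified in advance.

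The cost is two or three sentences, with no new data, visits or subjects. The downside is that the responder result is no longer reported as a small p-value, and any test of response needs a reference rate that someone must defend beforehand.
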